#### 6. STUDY CALENDAR

Baseline evaluations are to be conducted within approximately 30 days prior to initiation of radiation therapy. Patients will be evaluated at least weekly during the course of radiation therapy. Note that the study calendar is based on the ideal subject. The schedule should be followed as closely as realistically possible, but may be modified due to problems such as scheduling delays, conflicts such as clinic closure or poor weather conditions, or other unforeseeable events.

		Radi	Radiation Follow-			Up		
	Baseline 	Week 1	Week 2	Mo 6 Post RT	Mo 12 Post RT	Mo 18 Post RT	Mo 24 Post RT	Every 6 months until patient death
Demographics	Х							
Medical history	Х							
Physical Exam	Х			Х	X	Х	Х	Х
Vital signs	Х			X	X	X	Х	Х
Height & Weight	Х							
Performance status	Х	Х	Х	Х	X	Х	Х	Х
Neurocognitive testing 	Х			Х	Х			
Acute toxicity 	X	Х	X					
Late toxicity 	X			Х	X	X	Х	Х
Brain MRI	Х			Х	X	X	Х	
Chest X-ray	Х							
CT Simulation 	Х							
Quality of Life 	X			Х	X			
Radiation		Х	X		1			
Pregnancy test	Х							

Neurocognitive testing consists of the tests outlined in Section 2.2 and Section 2.3

RTOG Acute Morbidity Scoring Criteria

RTOG Late Morbidity Scoring Criteria

CT simulation without contrast will be performed and coregistered with T1 weighted MRI. Fused MRI may be the diagnostic MRI used prior to study entry or a dedicated treatment planning MRI.

EORTC Quality of Life Questionnaire (QLQ-C30), Brain Cancer Module 20 (BN20) Within approximately 30 days prior to registration

#### 7. MANAGEMENT OF TOXICITY

#### 7.1 Acute Toxicity

Acute morbidity potentially associated with therapy will be monitored and recorded on the Radiation Oncology On-Treatment Evaluation Form for all patients from baseline to 90 days after completion of radiation therapy. Grading will be according to the RTOG Acute Morbidity Scoring Criteria as follows:

Organ	Grade 0	Grade 1	Grade 2	Grade 3	Grade 4
Skin	No change over baseline	Faint erythema, epilation, dry desquamation, or decreased sweating	Tender or bright erythema, patchy moist desquamation, moderate erythema	Confluent, moist desquamation other than skin folds, pitting edema	Ulceration, hemorrhage, necrosis
Eye	No change over baseline	Mild conjunctivitis with or without scleral injection, increased tearing	Moderate conjunctivitis with or without keratitis requiring steroids and/or antibiotics, dry eye requiring artificial tears, iritis with photophobia	Severe keratitis with corneal ulceration, objective decrease in visual acuity or in visual fields, acute glaucoma, panopthalmitis	Loss of vision (unilateral or bilateral)
Ear	No change over baseline	Mild external otitis with erythema, pruritis, secondary to dry desquamation not requiring medication. Audiogram unchanged over baseline.	Moderate external otitis requiring topical medication, serous otitis media, hypoacusis on testing only	Severe external otitis with discharge or moist desquamation, symptomatic hypoacusis, tinnitus, not drug related	Deafness

CNS	No change over baseline	Fully functional status with minor	Neurologic findings present sufficient to	Neurologic findings requiring hospitalization	Serious neurologic impairment which included
		neurologic findings, no medications needed	require home care. Nursing care may be required. Medications including steroids and/or antiseizure agents	for initial management	paralysis, coma, or seizures, despite medications. Hospitalization required

#### 7.2 Late Toxicity

Late toxicity will be recorded on the Radiation Oncology Follow-up form at each follow-up visit greater than 90 days post completion of radiation therapy. Grading will be according to the RTOG Late Radiation Morbidity Scoring Schema as follows:

Organ	Grade 0	Grade 1	Grade 2	Grade 3	Grade 4	Grade 5
Skin	None	Slight atrophy, pigmentation change, some hair loss	Patchy atrophy, moderate telangiectasia, total hair loss	Marked atrophy, gross telangioectasia	Ulceration	Death directly related to late

Subcutaneous Tissue	None	Slight induration and loss of subcutaneous fat	Moderate fibrosis but asymptomatic. Slight field contracture. <10% linear reduction	Severe induration and loss of subcutaneous tissue. Field contracture >10% linear measurement	Necrosis	radiation effect
Spinal Cord	None	Mild L'Hermitte's syndrome	Severe L'Hermitte's syndrome	Objective neurologic findings at or below cord level treated	Mono-, para-, quadra-plegia	
Brain	None	Mild headache, slight lethargy	Moderate headache, great lethargy	Severe headaches, severe CNS dysfunction (partial loss of power or dyskinesia)	Seizures, paralysis, coma	
Еуе	None	Asymptomatic cataract, minor corneal ulceration of keratitis	Symptomatic cataract, moderate corneal ulceration, minor retinopathy or glaucoma	Severe keratitis, severe, retinopathy or detachment, severe glaucoma	Panopthalmitis, blindness	

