#### 5.1.6 Risks of Radiation

Short term toxicities of radiation therapy include fatigue, alopecia, erythema or irritation of the skin, dry skin, headaches, worsening of current symptoms, edema of brain requiring steroids, ear pain or discomfort, damage to the baby if patient is or becomes pregnant, seizures, neurologic deficits depending on tumor location, edema of brain requiring surgery, death. Long term toxicities include memory loss, cataracts, edema of the brain requiring steroids, vision loss, hearing loss, necrosis of brain requiring surgery second tumor or cancer caused by radiation.

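### Hearing loss is a named long-term toxicity, but the printed late scale has no hearing item, so late hearing loss is likely to be under-ascertained (minor)

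*Combined protocol and SAP*

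**What the plan says.** Section 5.1.6 separates short-term from long-term risks. The long-term list reads: "Long term toxicities include memory loss, cataracts, edema of the brain requiring steroids, vision loss, hearing loss, necrosis of brain requiring surgery", and it ends with second tumors. The short-term list includes ear pain or discomfort but not hearing loss.

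Section 7.1 prints the acute scale with rows for skin, eye, ear and CNS. The ear row grades hearing: Grade 2 is "Moderate external otitis requiring topical medication, serous otitis media, hypoacusis on testing only", Grade 3 is "Severe external otitis with discharge or moist desquamation, symptomatic hypoacusis, tinnitus, not drug related", and Grade 4 is deafness. This scale applies "for all patients from baseline to 90 days after completion of radiation therapy". The calendar in Section 6 marks it at baseline, week 1 and week 2.

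After that the late scale takes over. Section 7.2 states: "Late toxicity will be recorded on the Radiation Oncology Follow-up form at each follow-up visit greater than 90 days post completion of radiation therapy". It continues: "Grading will be according to the RTOG Late Radiation Morbidity Scoring Schema as follows". The five rows that follow are skin, subcutaneous tissue, spinal cord, brain and eye. The calendar cites the "RTOG Late Morbidity Scoring Criteria" and marks late toxicity at baseline, at months 6, 12, 18 and 24, and every six months thereafter.

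Three other provisions matter. Section 9.1 defines an adverse event broadly and includes events after exposure. Section 9.2 has radiation-related events entered on the toxicity case report forms. Section 8.4 reports adverse events in frequency tables using CTCAE v4.0.

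**The concern.** The protocol itself expects hearing loss as a late effect, yet the scheduled late scoring does not ask about it. The organs on the late scale get a grade at every follow-up visit, including Grade 0 when nothing is found. Hearing gets no grade, so an absence of recorded events cannot be told apart from an absence of inquiry.

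What is at stake is the completeness of the description of late harm after hippocampal-sparing PCI, and its comparability across organs. There is also a small side effect on interpretation. The Brief Test of Attention (Section 2.3.3) relies on lists read aloud and is repeated at months 6 and 12. An unrecorded hearing loss could be mistaken for reduced attention on that test. The test is not part of the primary endpoint or of the composite in Section 8.1.3.2, so this does not reach the main analyses.

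**Working it through.** The plan gives no figure to reproduce. The check compares the listed long-term harms with what is scheduled after day 90.

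**Step 1: each long-term harm in Section 5.1.6 against scheduled measures (Sections 6 and 7.2, and the quality-of-life forms).**

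| Long-term harm | Scheduled measure after day 90 |
|---|---|
| Memory loss | Neurocognitive tests, months 6 and 12 |
| Cataract, vision loss | Eye row at every late visit; BN20 items 36 to 38 at months 6 and 12 |
| Brain edema, brain necrosis | Brain row at every late visit; MRI at months 6, 12, 18 and 24 |
| Hearing loss | None |
| Second tumor or cancer | No row; brain MRI to month 24 could show only an intracranial one |

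**Step 2: can another row absorb hearing?** The brain row grades headache, lethargy, CNS dysfunction described as loss of power or dyskinesia, seizures, paralysis and coma. Hearing is in none of its grades, nor in the other four rows.

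**Step 3: is hearing asked about elsewhere?** The calendar has no audiogram. Medical history is marked at baseline only. Physical examination is marked at each late visit, but no hearing check is specified. The QLQ-C30 and BN20 contain no hearing question.

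**Step 4: count the scheduled scoring.** The calendar marks the acute ear row at 3 points (baseline, weeks 1 and 2). The text of Section 7.1 extends acute recording to day 90, but no visit is scheduled between week 2 and month 6. Late visits in the first two years number 4 (months 6, 12, 18, 24), and 0 of the 4 carry a hearing item. The same holds for every later visit.

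**Step 5: what the general route requires.** For late hearing loss to appear in the CTCAE v4.0 tables by way of Section 9.2, it must be volunteered or noticed and then judged related to radiation. Section 5.2 lets follow-up visits take place at outside hospitals with records sent in, where unprompted capture is less dependable. The plan collects toxicity on RTOG scales but reports on CTCAE v4.0, and does not say how the two are combined.

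**Step 6: size.** If a fraction c of late hearing losses is captured this way, the share missed is 1 − c, whatever the true rate. The documents give neither c nor a late hearing-loss rate, so no numerical shortfall can be stated.

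**The case against.** The strongest reply is that late hearing loss is already covered. The adverse event definition includes events after exposure, Section 9.2 calls for all radiation-related events to be recorded, and Section 8.4 reports on CTCAE v4.0. None of these has an organ limit or a 90-day cut-off. Radiation-related deafness at month 12 would have to be recorded and should appear in the tables. This stands, and it rules out two stronger readings that a reader might infer: that the late safety profile will look falsely clean, and that late hearing loss could not be graded at all. It does not make the general route equivalent to scoring at each visit.

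A reader might also infer that hearing is the only late harm left off the scale. It is not: second cancers have no row either, and MRI covers them only in part.

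Nor is the acute ear row misplaced. It largely grades otitis, which fits the ear discomfort listed as a short-term risk.

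Finally, one might treat the missing item as zero events in 125 patients and attach an upper confidence bound. The plan does not support that: an organ that is not on the scale yields no result rather than a zero, and no ear-toxicity proportion is planned.

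Two limits on the evidence remain. The follow-up form is not reproduced and may carry a prompt that the protocol does not show. The table was read from a PDF, so a lost row cannot be fully excluded, although the five rows look complete.

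**Conclusion.** The point holds as one of under-ascertainment. A harm that the protocol names as long-term has no scheduled item from month 6 on, and its capture depends on unprompted reporting and attribution to radiation. Late hearing loss is therefore likely to be recorded less completely than effects in the five scored organs.

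Severity is minor. Late toxicity is neither an objective in Section 1 nor an endpoint in Section 8.1. The primary test, the sample size and the brain-metastasis stopping rule are untouched. The conclusion assumes that the late table is complete as printed and that the follow-up form follows it. If the form already asks about hearing, only the wording of Section 7.2 needs to change.

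**What to change.** Add a history-based ear/hearing item to the late scoring in Section 7.2 and to the follow-up form, completed at month 6 and at each later visit. Grade it with CTCAE v4.0, which Section 8.4 already names for reporting, or with the hearing descriptors in the acute ear row. Record baseline on the same grading so that change can be read directly; the calendar already marks both toxicity scales at baseline. Report the item by grade in the adverse event table, and add a sentence saying how RTOG-scored and CTCAE-reported data are combined.

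The cost is one line on an existing form and a wording amendment. No audiogram, new visit or extra staff is needed. There are two drawbacks: grading by history misses subclinical loss, and the item is an addition to the late scale as printed, so it should be labelled as such in the report.

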#### 8. STATISTICAL CONSIDERATIONS

#### 8.1 Study Design/Endpoints

#### 8.1.1 Study Design

This is a single-arm phase II prospective study of patients with limited stage SCLC to evaluate neurocognitive outcomes following hippocampal-sparing PCI (25 Gy in 10 fractions) relative to a historical control receiving standard PCI (RTOG 0212 arm receiving 25 Gy in 10 fractions).

#### 8.1.2 Primary Endpoint

The primary endpoint for this study is cognitive function, specifically memory, six months from the completion of PCI as measured by the HVLTR-delayed recall.

#### 8.1.3 Secondary Endpoints

- 8.1.3.1 Cognitive function, specifically memory, at 12 months from PCI as measured by the HVLT-R delayed recall
- 8.1.3.2 A composite cognitive function endpoint using the validated Reliable Change Index (48,49) to include the Controlled Word Association Test (COWAT), the HVLT-R-delayed recall, the HVLT-R-trials 1-3 and Trail Making Tests part A and B (TMT)
- 8.1.3.3 Quality of Life (QOL) as measured using the EORTC Quality of Life Questionnaire (QLQ-C30) and Brain Cancer Module 20 (BN20) at baseline, 6 months, and 12 months
- 8.1.3.4 Development of brain metastases at 2 years following completion of radiation therapy will be coded as a binary variable (yes or no)

8.1.3.5 Development of leptomeningeal carcinomatosis at 2 years following completion of radiation therapy will be coded as a binary variable (yes or no)

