#### **1.2** Secondary Objectives

- 1.2.1 Evaluate performance on HVLT-R delayed recall at 12 months following hippocampal-sparing PCI relative to historical control receiving standard PCI.
- 1.2.2 Evaluate composite cognitive function at 6 and 12 months following hippocampal-sparing PCI relative to a historical control receiving standard PCI
- 1.2.3 Evaluate quality of life following hippocampal-sparing PCI relative to a historical control receiving standard PCI.
- 1.2.4 Determine whether development of brain metastases following hippocampalsparing PCI is higher than expected.
- 1.2.5 Determine whether development of leptomeningeal carcinomatosis following hippocampal sparing PCI is higher than expected
- 1.2.6 Evaluate overall survival following hippocampal sparing PCI.

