#### 5.3 Criteria for Removal from Study

Patients will be removed from the study for the following reasons:

- 5.3.1 Unacceptable toxicity from therapy. Toxicity must be appropriately documented.
- 5.3.2 Development of intercurrent, non-cancer related illness that prevents either continuation of therapy or regular follow-up.
- 5.3.3 The patient may decide to discontinue enrollment in the protocol at any time and for any reason.

All reasons for discontinuation of treatment must be documented.

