The Reliable Change Index will measure meaningful change between baseline and 6 and 12 months for HVLT–R, Trail Making Test part A and B, COWAT. The Reliable Change Index is derived from the standard error of measurement (SEM) for each test in the battery. The SEM is calculated from the test–retest reliability (r) and the standard deviation of test scores (SD): SEM=sqrt[SD×(1-r)]. The standard error of the difference (SEdiff) is then calculated as SEdiff =sqrt[ $2\times(SEM)^2$ ]. For each test in the neurocognitve battery, the Reliable Change Index value will be determined *a priori* for that particular test to determine whether a change from baseline is clinically meaningful.

We will compute summary statistics and compare our patients to the historical controls based on tests that are appropriate for the type of data.

[figure not shown]
Quality of Life on our study will be assessed using EORTC Quality of Life questionnaire (QLQ-C30) and the Brain Cancer Module 20 (BN 20) pre-therapy, at 6 months, and at 12 months after therapy. For each module, summary statistics of the scores will be reported for each study time point. Change scores in quality of life from pre-therapy to post-therapy will be calculated and tested via paired t-tests for the hippocampal-sparing PCI treatment group. We may fit mixed-effect models to explore changes in quality of life assessments over time.

We will tabulate development of brain metastases within 0.5 mm of the hippocampus. We will report adverse events based on CTCAE v4.0 by frequency tables. We will test the proportion of patients who develop brain metastases via binomial test. Overall survival will be measured from the start of treatment to death or last followup. For subjects who alive or lost follow up at the end of study, overall survival will be censored at the last follow up date. Overall survival probabilities will be estimated via the Kaplan-Meier method; median survival and 95% confidence interval via Greenwood's formula for variance will be reported.

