#### 8.5 Safety Monitoring

We have included a formal statistical stopping rule for monitoring the occurrence of brain metastases. The article describing RTOG 0212 reported that the raw proportion of patients with brain metastases is 22% (29/131) at 1 year for the group getting 2.5 Gy in 10 fractions. We established a monitoring rule that will recommend considering stopping the study if there appears to be high probability that the risk of brain metastasis at 1 year is above 22%. Specifically, if the posterior probability that the risk exceeds 25% of brain metastasis by 1 year after treatment is 75% or greater (3:1 odds), then we will consider stopping the study. In this calculation, the number of patients with brain metastasis at 1 year is a binomial random variable. The prior

distribution for the risk of brain metastasis by 1 year is beta with parameters 29 & 102. Although we can apply the stopping rule calculation after every patient, we may monitor in batches of 10. The stopping rule is illustrated in the figure below.

Safety Monitoring Boundary

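### The 2-year brain-metastasis test has no 2-year expected rate to test against, and patients without full 2-year follow-up have no valid yes/no code

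*Combined protocol and SAP*

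**What the plan says.** Objective 1.2.4 is to "Determine whether development of brain metastases following hippocampalsparing PCI is higher than expected", and objective 1.2.5 is to "Determine whether development of leptomeningeal carcinomatosis following hippocampal sparing PCI is higher than expected". Section 8.1.3 turns both into 2-year yes/no variables: "Development of brain metastases at 2 years following completion of radiation therapy will be coded as a binary variable (yes or no" for brain metastases and "Development of leptomeningeal carcinomatosis at 2 years following completion of radiation therapy will be coded as a binary variable (yes or no" for leptomeningeal disease.

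The whole description of the brain-metastasis test is one sentence in 8.4: "We will test the proportion of patients who develop brain metastases via binomial test". It gives no null proportion, significance level, direction or denominator. No test is described for leptomeningeal disease.

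The only historical brain-metastasis figure is in 8.5, where "the raw proportion of patients with brain metastases is 22% (29/131) at 1 year" supplies the prior, beta with parameters 29 and 102, for a 1-year stopping rule. The 25% in that section is a 1-year monitoring threshold, not an expected 2-year rate.

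Follow-up can end early. Section 5.3 states that "The patient may decide to discontinue enrollment in the protocol at any time and for any reason", and 5.2 follows patients until death or the time of data analysis. The one rule for incomplete follow-up, in 8.4, concerns survival: "overall survival will be censored at the last follow up date".

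**The concern.** Asking whether a rate exceeds expectation needs an expected rate at the same time point. The endpoint is at 2 years and the only benchmark is at 1 year. The analyst must either find a 2-year RTOG 0212 rate that the plan does not give or fall back on 22%. The second choice sets two years of events in the new cohort against one year of events in the old.

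The coding gap pulls the other way. A patient last imaged free of metastasis at 10 months is neither a yes nor a no at 2 years. Counting such patients as event-free lowers the observed rate and can hide an excess.

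Hippocampal sparing deliberately lowers the dose to part of the brain, so this is the main oncologic safety question at the end of the study. As written, its answer depends on choices that could be made after the data are seen.

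**Working it through.** **Inputs**
- Historical rate: 29/131 at 1 year (8.5).
- n = 125: planned enrolment (8.2.1), taken here as fully evaluable (assumption).
- One-sided 5%: assumption for this endpoint; 8.2.1 states it for the primary test only.
- True 2-year risks of 25%, 28% and 30%: assumptions, because the documents give none.

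**1. The plan's own figure.** 29/131 = 22.1%, which is also the prior mean 29/(29 + 102). The stated 22% reproduces. Its exact (Clopper-Pearson) 95% CI is 15.4% to 30.2%.

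**2. The 1-year rate used as a 2-year null.** Find the smallest k with P(Bin(125, 0.22) ≥ k) ≤ 0.05. The tail is 0.068 at 35 and 0.045 at 36, so the test rejects at 36 or more (36/125 = 28.8%). With 29/131 as the null, the boundary is again 36 (size 0.049). If the technique adds no risk and the 2-year risk under either method is p, the chance of declaring it worse is P(Bin(125, p) ≥ 36):

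| Assumed 2-year risk p | Declared worse |
|---|---|
| 25% | 0.189 |
| 28% | 0.455 |
| 30% | 0.648 |

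**3. Coding of incomplete follow-up.** Suppose 28 metastases are seen among 125.
- All unknowns coded no: 28/125 = 22.4%, one-sided p = 0.51 against 29/131.
- Eight lost patients coded yes: (28 + 8)/125 = 36/125 = 28.8%, p = 0.049, exactly at the boundary.
- Exclusion instead, if 38 patients die or are lost event-free: 28/87 = 32.2%, p = 0.020.

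The counts are invented. They show only that the unstated choice can change the conclusion.

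**4. A matched comparison at 1 year.** Treating 29/131 as a known constant ignores its sampling error. With both cohorts truly at 22%, a nominal 5% exact test then declares the new one worse 11.8% of the time. A two-sample comparison (125 v 131) allows for that error:
- Pooled score test at 40: pooled proportion 69/256 = 0.2695; difference 0.3200 − 0.2214 = 0.0986; standard error √[0.2695 × 0.7305 × (1/125 + 1/131)] = 0.0555; z = 1.78. At 39, z = 1.641, just short of 1.645. Boundary 40 (32.0%).
- Fisher's exact test: p = 0.0507 at 40 and 0.0380 at 41. Boundary 41 (32.8%).
- Section 8.5 rule at n = 125: the posterior is Beta(29 + k, 102 + 125 − k), and P(risk > 25%) is 0.709 at k = 39 and 0.756 at k = 40. It first reaches 75% at 40, the same cut-off as the score test.

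Power at these boundaries, given the observed 29/131, is P(Bin(125, p) ≥ k):

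| True 1-year risk | Fixed 22% null (36) | Score (40) | Fisher (41) |
|---|---|---|---|
| 30% | 65% | 34% | 28% |
| 33% | 86% | 63% | 55% |

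**The case against.** **The horizon is stated.** A reader of 8.4 alone might infer that the test has no time point. Section 8.1.3.4 fixes it at 2 years and 8.4 merely does not repeat it. That objection stands; what is missing is the null at that horizon.

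**No passage proposes 22% as the 2-year null.** A reader might infer that the plan tests 2-year events against a 1-year rate. It does not say so: the 22% appears only in the monitoring section. The error rates in step 2 are therefore conditional on a misuse, not properties of the written plan. This also stands, but no other benchmark is offered, so the test still cannot be run as written.

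**Section 8.5 already covers 1-year risk.** It uses the same 29/131, carries its uncertainty through the prior, and at 125 patients with complete 1-year data has the same cut-off as a score test. A new 1-year test would therefore add little. But 8.5 is a rule for considering whether to stop, and it does not answer the 2-year question.

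**The point is secondary and loss may be small.** This is one of six secondary objectives in a single-arm phase II trial. Eligibility requires that long-term follow-up be possible (3.1.12), outside MRIs are accepted (5.2), and metastases near the hippocampus are tabulated (8.4). This lowers the severity. It does not supply a code for patients whose 2-year status is unknown.

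**Conclusion.** The point holds in limited form. The plan sets a 2-year endpoint and a binomial test, gives an expected rate only at 1 year, and has no rule for patients lost or not yet followed to 2 years free of metastasis. Objective 1.2.4 cannot be answered validly until these are settled. Objective 1.2.5 has the same coding gap, and neither an expected rate nor a test.

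These findings rest on the text alone. The 19%, 45% and 65% rest on four assumptions: the borrowed 1-year null, a one-sided 5% level, 125 evaluable patients, and the chosen 2-year risks. They show what a mismatched benchmark could do and do not predict this trial's error rate. Likewise, the eight-patient example contrasts two extremes and does not estimate bias.

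It would be wrong to infer that the trial's main conclusion or its safety monitoring is compromised. The primary HVLT-R test does not use this endpoint, and the stopping rule sets a 1-year risk against a 1-year rate. The change should be made, but it is not critical.

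**What to change.** In 8.4:

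1. Estimate the 2-year brain-metastasis and leptomeningeal rates by cumulative incidence with 95% CI. Treat death without the event as a competing event and censor at last brain imaging.
2. Test formally against RTOG 0212 only at a matching horizon. Test at 2 years only if a 2-year RTOG 0212 rate and its denominator are obtained and stated. Otherwise report the 2-year rate descriptively and make any formal comparison with 29/131 at 1 year, allowing for its sampling error. Acknowledge that the 8.5 rule already does this, with its boundary at 40 of 125.
3. For any test, state the null, level, direction and denominator, and how a death free of metastasis is coded. Code losses both ways, all no and all yes, as a sensitivity analysis.

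**Cost.** This is SAP wording and a standard competing-risks estimate, using MRIs already scheduled every 6 months for 2 years. The real price is power. At a true 1-year risk of 30%, a fixed 22% null would detect the excess 65% of the time, against 34% (score) or 28% (Fisher) for the two-sample tests; at 33% the figures are 86%, 63% and 55%. A 1-year test also leaves second-year events to description only. A 2-year test needs a figure the documents do not contain. Before any comparison, it must be confirmed whether 131 counts all treated or only evaluable patients.
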